### **10.2: Discontinuation related to the study question**

If patient discontinue the study of reasons related or might be related to the trial treatment will be classified as "Withdrawal". These will not be replaced by new participants but included in both the Per-Protocol (PP) and the ITT analysis using the procedure "Last observations carried forward" (LOCF).

## **XI Statistical Model**

### **11.1 Presentation of results**

Assumed continuously distributed variables expresses by mean values with 95% confidence intervals . As an index of dispersion Standard Deviation (SD) will be used.

Categorized variables will be expressed in Contingency Tables 

### **11.2 Statistical methods**

The differences between the groups will be considered significant if the p-value is less or equal to 5 %. Comparison between groups regarding assumed continuously distributed variables will be performed by using analyses of covariance (ANCOVA) with a basic observation as covariance and repeated measurements . Contingency table analyses will be used for comparison of discrete distributed variables. . Correlation and regression analysis will be performed to estimate the connection in the development between variables.

### **11.3 Power analysis and sample size determination**

With a significance level of 5 %, detection power level of 95 %, and a clinical relevance difference defined as 1xSD of BMD, the number of patients included in each group will be at least 24 patients in each group finalizing the study .

Based on our previous study on cross country skier (XCS), the Coefficient of Variance (CV) in total BMD was found to be 0.07 with SD = 0.09 g/cm^2 for both sexes . It is reasonable to assume that the variation in BMD among elderly patients is below the dispersion in young active XCS. Daily intake of Jarlsberg cheese during 12 weeks in XCS detected a significant increase in BMD of 0.1 g/cm^2. Vitamin D + Ca is recommended to reduces bone loss, but it is reasonable to assume none or limited increase in BMD. From these results it is reasonable to define a clinically relevant difference between the group of 1xSD=0.09 g/cm^2. To correct for the multicentre situation and drop-out rate, 30 patients in each group must be included .

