### 1.8.2 Clinical part

The patients will be allocated (1:1) to vitamin D + Ca-tablets  $\pm$  Jarlsberg cheese. All the participants will get new delivery of vitamin D and Ca-tablets every four weeks. The patients allocated to Jarlsberg will additionally receive Jarlsberg cheese. The patients will receive a compliance & activity form and asked to fill in every day. All the patients meet for new visits at week 4, week 16, and week 32. Patients allocated to only vitamin D + Ca tablets at baseline well additionally meet for visits at week 20 and week 48. At all these visits blood samples for

measurement of Osteocalcin, CTX-1, PINP, BALP and PTH will be drawn fasting in the morning, and concomitant medication and treatment compliance recorded. The main visits will be performed every 16 weeks. New DXA screening will be performed. Patients obtaining a BMD T-score  $\leq -2.5$  will discontinue the study and switched to antiresorptive treatment plus daily OED of Jarlsberg cheese. The daily food intake during four consecutively days will be recorded on the Diet-App. Blood samples for measurements of Osteocalcin, CTX-1, PINP, BALB and PTH will be drawn fastening in the morning at every visits. Furthermore, blood samples for measuring and biochemical variables, HbA1C and Lipids, will be recorded. The CTCAE will be recorded as well. The visit at Week 32 and Week 48 will be the last observation in the study for the patients initially allocated to Jarlsberg and controls, respectively. In addition to the mentioned variables blood samples for measurement of Interleukins and Cytokines will be performed. All the patients completed the study will be offered to continue the daily intake of Jarlsberg cheese. These patients will be followed up one year after the last visit with a new DXA and a blood sampling for measurements of the Osteocalcin level and the bone markers PINP, CTX and BALP.

**1.9: Sample size:** With a significance level of 5%, a power of 90% and a Clinically Relevant Difference (CRD) of one time the Standard Deviation in change of BMD, at least 24 patients in each group must finalize the study. With an expected drop-out rate of 25%, 30 patients in each group must be included.

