### **10.1: Discontinuation not related to the study question**

If patient discontinue the study of administrative reasons or reasons documented not related to the trial treatment will be classified as "Drop out" and replaced by new participant. The dropouts will be described specially in the statistical analysis.

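### Sections 1.9 and 11.3 attach 90% and 95% power to the same 24 finishers per group, and 30 enrolled covers 20% unreplaced loss, not the stated 25%

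*Protocol*

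**What the plan says.** The protocol gives the sample size twice.

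- **Section 1.9 (synopsis):** "With a significance level of 5%, a power of 90% and a Clinically Relevant Difference (CRD) of one time the Standard Deviation in change". The outcome meant there is BMD, and the resulting requirement is that "at least 24 patients in each group must finalize the study". It then adds: "With an expected drop-out rate of 25%, 30 patients in each group must be included".
- **Section 11.3:** "With a significance level of 5 %, detection power level of 95 %, and a clinical relevance difference defined as 1xSD of BMD". Its requirement for finishers is the same: "the number of patients included in each group will be at least 24 patients in each group finalizing the study". The enrolment figure follows: "To correct for the multicentre situation and drop-out rate, 30 patients in each group must be included".

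Three other sections bear on these figures.

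- **Section 11.2** plans the group comparison by "analyses of covariance (ANCOVA) with a basic observation as covariance and repeated measurements".
- **Section 10.1** says that a patient who leaves for reasons unrelated to the trial treatment is classed as a drop-out "and replaced by new participant".
- **Section 10.2** says that patients who leave for reasons that are, or might be, treatment-related are not replaced. They stay in both the per-protocol and ITT analyses by last observation carried forward (LOCF).

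**The concern.** The two sections share the significance level, a standardised difference of 1 and the number of finishers, but they state different powers. The planned type II error is 10% in one place and 5% in the other, and a reader or an ethics committee cannot tell which was intended.

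The step from 24 finishers to 30 enrolled does not match a 25% loss. Taken at face value, the enrolment target does not deliver the minimum number of finishers that the protocol sets for itself. Section 1.9 explains the whole step by drop-out, whereas Section 11.3 explains the same step by drop-out and the multicentre setting together.

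**Working it through.** **Inputs**

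| Input | Value | Source |
|---|---|---|
| Significance level | 5%, sidedness not stated (two-sided taken, one-sided also tried) | 1.9, 11.3 |
| Standardised difference d | 1 (one SD) | 1.9, 11.3 |
| Finishers per group | 24 | 1.9, 11.3 |
| Power | 90% / 95% | 1.9 / 11.3 |
| Drop-out rate | 25% | 1.9 |
| Enrolled per group | 30 | 1.9, 11.3 |

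**Number needed for each power.** The normal approximation is n = 2(z₀.₉₇₅ + z_power)²/d² per group.

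- 90%: 2 × (1.960 + 1.282)² = 21.01, so 22.
- 95%: 2 × (1.960 + 1.645)² = 25.99, so 26.

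The stated 24 lies between the two.

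**Power by two-sided t-test.** This uses the noncentral t with 2n − 2 degrees of freedom and noncentrality d√(n/2).

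| n per group | Power |
|---|---|
| 22 | 90.0% (0.8997) |
| 23 | 91.2% |
| 24 | 92.4% |
| 26 | 94.2% |
| 27 | 95.0% |

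The smallest n is 23 for 90% and 27 for 95%. With 24 per group, 90% power corresponds to a difference of 0.96 SD and 95% to 1.06 SD.

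**What would give 95% at 24**

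- A one-sided 5% test gives 96.1%.
- ANCOVA on baseline multiplies the error variance by 1 − r² when the SD is that of BMD itself, as in Section 11.3. With 45 degrees of freedom, r = 0.35 gives 95.1%, so a correlation of about 0.35 or more is needed.
- If the SD is that of the change, as in Section 1.9, the factor is (1 + r)/2, assuming equal variances at both times. The condition then reverses: r must be about 0.76 or less (r = 0.75 gives 95.2%, r = 0.80 gives 94.7%).

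The protocol gives no correlation, so these values of r are assumptions.

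**Drop-out step**

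- Finishers from 30 at 25% unreplaced loss: 30 × (1 − 0.25) = 22.5, which is 1.5 per group short of 24.
- Loss at which 30 leaves 24: 1 − 24/30 = 20%.
- Enrolment for 24 finishers at 25% loss: 24/(1 − 0.25) = 32.
- The stated figure is reproduced by 24 × 1.25 = 30, which adds 25% of the finishers and not 25% of those enrolled.
- For 27 finishers (95%, unadjusted and two-sided): 27/0.75 = 36.

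**With replacement.** Let a share f of losses be replaced, and let replacements be lost at the same 25%. Expected finishers are then 30 × 0.75/(1 − 0.25f).

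- f = 0 gives 22.5.
- f = 0.25 gives 24.0.
- f = 0.5 gives 25.7.

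The protocol gives no f; these are assumed values.

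**Multicentre correction.** Adding 25% to 24 uses all 30, and dividing by 0.75 needs 32. Either way, nothing within 30 is left for the multicentre correction named in Section 11.3.

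**The case against.** The strongest point is replacement. Section 10.1 uses drop-out as a defined class whose members are replaced. If the 25% in Section 1.9 means that class, the 22.5 does not arise. This is fair, and it is why the shortfall is stated for unreplaced loss only. But Section 1.9 does not say which losses the 25% covers, and Section 10.2 leaves treatment-related withdrawals unreplaced. If every loss in the 25% were replaced, the protocol would still have to say why enrolment is inflated for it.

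LOCF keeps withdrawals in the analysis, so the number analysed may exceed the number of finishers. That also stands, and it means that the power quoted for 22 to 23 finishers is not exactly the power of the planned analysis. It does not meet the requirement as written, which counts patients who complete the study.

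The two sections define the SD differently (of BMD, and of change in BMD), so one SD is not the same clinical difference in each, and ANCOVA would gain differently on the two scales. This does not reconcile the powers. Each section sets d = 1 on its own scale, and neither invokes ANCOVA in the sample size. It is one more item to align.

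Finally, the protocol does not itself write 24 × 1.25, and it cites references for the sample size and the multicentre correction that are not at hand. How 30 was reached is therefore inferred. That 30 is too few for 25% unreplaced loss does not depend on the inference.

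**Conclusion.** The point holds. The 90% and 95% statements conflict whatever the sidedness. Under a two-sided unadjusted t-test at d = 1, 24 finishers give 92.4%, which is enough for 90% and three per group short of the 27 needed for 95%. A one-sided test or a suitable baseline correlation would reach 95% at 24, but the sample size sections state neither.

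The enrolment of 30 per group covers 20% unreplaced loss. At the stated 25% it falls 1.5 finishers per group below the protocol's own minimum, unless about a quarter of losses are replaced.

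The consequence for the trial is modest: even 22 to 23 finishers give about 90% power for a one-SD difference, which is the target in Section 1.9. This is an error of statement that should be corrected. It does not show that the trial is underpowered at 90%.

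**What to change.** 1. State one power in Sections 1.9 and 11.3, with the sidedness. As written, 24 finishers support 90% at two-sided 5% for a one-SD difference, with actual power of about 92%. Keep 95% only if the assumption behind it (one-sided test, or baseline correlation with the SD scale it refers to) is written down.
2. Use one SD definition in both sections: SD of BMD or SD of the change in BMD.
3. Calculate the drop-out step as finishers divided by (1 − loss rate), and say which losses the 25% covers under Sections 10.1 and 10.2. Then choose one of three options:
   - keep 30 and state that 25% unreplaced loss leaves 22 to 23 finishers and about 90% power;
   - keep 30 and explain how replacement brings the finishers to 24;
   - enrol 32 per group.
4. Show the drop-out and multicentre components of the step from 24 to 30 separately.

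If 30 is kept, this costs wording only. If 24 finishers must be secured at 25% unreplaced loss, it costs two more patients per group, four in total.

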## **XII: Operational Matter**

### **12.1: Investigator's agreement**

Before the start of the trial the investigator will confirm the agreement to participate in the trial by signing the Investigator's Agreement Form (Appendix IX).

### **12.2: Instructions**

The investigators will give instructions by the data manager group and the clinical monitor supported by the project manager at the start-up visit and during the study.

### **12.3: Amendments to the protocol**

Changes in the protocol can be required by the Ethical Committee, project manager or TINE. Changes must be written in amendments approved by the steering committee, investigator, TINE and Ethical Committee. Amendments must be numbered and be together with the original protocol.

It is forbidden to add new parameters consisting of measurements on the patients in the study unless they are covered as amendments in the protocol or taken due to the health and safety of the patient.

### **12.4: Protocol deviations**

Deviations from the protocol should be restricted as much as possible and will be fully recorded and justified. The Project manager will be informed as soon as possible of all protocol deviations.

### **12.5: Compliance monitoring**

The Project manager and the Investigator will ensure that the site is suitable for the trial and that the participants are well informed of the particulars of the trial. The Project manager and Investigators should check, protocol compliance, handling of the test articles and recording of data during the critical stages of the trial. A report is prepared of each visit and kept in the trial master file (TMF).

### **12.6: Responsibilities**

The investigator will acknowledge the responsibilities and the agreement to participate in the trial by dating and signing the agreement form. The Project manager will verify that adequate arrangements have been made for the observations, measurements and recording of the data.

### **12.7: Confidentiality**

The obtained data and results will be used by TINE for marketing purpose. The main study database will be stored in the product database of TINE.

The steering committee has the demand and the right to try the results published in an international medical journal. The draft of the manuscript must be presented for the sponsor for comments, discussion and final approve. The sponsor cannot stop the publication unless it is proved that publication of the results may destroy for marketing of the product.

The results from the study cannot be presented in any meeting or congresses without approval by the sponsor. The data obtained in this study must be handled confidentially by the member of the steering committee until the first registration of the product is performed.

## **XIV Appendix**

**14.1: Serious Adverse Event Form**

**14.2: The set of CRF's**

**14.3: Monitoring report form**

**14.4: CV investigators and study coordinators**

**14.5: Patient information**
